8.1 Baseline Screening for SARS-CoV-2 antibodies

A blood sample will be obtained before study enrollment to exclude from participation individuals with evidence of SARS-CoV-2 antibodies by a lateral flow immunoassay.

8.2 Efficacy and Immunogenicity Assessments

8.2.1 Immunogenicity Assessments

8.2.1.1 SARS-CoV-2 Neutralizing Antibody Assessment

SARS-CoV-2 neutralizing antibodies will be measured using a neutralization assay.

Serum samples are mixed with constant concentration of the SARS-CoV2 virus. A reduction in virus infectivity (viral antigen production) due to neutralization by antibody present in serum samples can be detected by ELISA. After washing and fixation, SARS-CoV-2 antigen production in cells can be detected by successive incubations with an anti-SARS-CoV-2-specific antibody, horseradish peroxide (HRP) Immunoglobulin G (IgG) conjugate, and a chromogenic substrate. The resulting optical density (OD) is measured using a microplate reader. The reduction in SARS-CoV-2 infectivity as compared to that in the virus control wells constitutes a positive neutralization reaction indicating the presence of neutralizing antibodies in the serum sample.

8.2.1.2 SARS-CoV-2 Spike Protein Antibody Serum IgG ELISA

SARS-CoV-2 anti-S protein IgG antibodies will be measured using an ELISA. Microtiter plates will be coated with SARS-CoV-2 Spike protein antigen diluted in coating buffer to the optimal concentration.

Plates may be blocked by the addition of a blocking buffer to all wells and incubation for a defined period. Following incubation, plates will be washed. All controls, reference, and samples will be pre-diluted with dilution buffer. The pre-diluted controls, reference and samples will then be further serially diluted in the wells of the coated test plate.

The plates will be incubated for a defined period. Following incubation, plates will be washed, an optimized dilution of goat anti-human IgG enzyme conjugate will be added to all wells, and plates will be further incubated. Following this incubation, the plates will be washed, and enzyme substrate solution will be added to all wells. Plates will be incubated for a defined period to allow the substrate to develop. Substrate development will be stopped by the addition of a stop solution to each well. An ELISA microtiter plate reader will be used to read the test plates using assay specific SoftMax Pro templates.

The average OD value for the plate blank will be subtracted from all the ODs within each plate. The sample titers will be derived using the measured values of the blanks, controls, and the reference standard curve, which will be included on each assay plate within the run.

8.2.1.3 Cellular-Mediated Immunity (using whole blood)

Cytokines will be measured in whole blood following stimulation with full-length S protein and/or pools of S-antigen peptides.

8.2.2 Efficacy Assessments

8.2.2.1 Definitions

COVID-19-like illness

Symptoms of COVID-19-like illness are as listed below, along with an accompanying tabulation of terms used in the CRFs versus diary cards / memory aids ([Table 8.2](#)).

Any ONE of the following (that persist for a period of at least 12 hours or reoccur within a 12-hour period):

- Cough (dry or productive)
- Fever
- Anosmia
- Ageusia
- Chillblains (COVID-toes)
- Difficulty breathing or shortness of breath
- Clinical or radiographic evidence of pneumonia
- Any hospitalization with the following clinical diagnosis:
 - Stroke, myocarditis, myocardial infarction
 - Thromboembolic event (blood clots [eg, pulmonary embolism, deep vein thrombosis, stroke])
 - Purpura fulminans

OR

Any TWO of the following (that persist for a period of at least 12 hours or reoccur within a 12-hour period):

- Pharyngitis
- Chills
- Myalgia
- Headache
- Rhinorrhea
- Abdominal pain
- At least one of nausea, diarrhea, vomiting

Table 8.2: COVID-19-like illness symptoms: CRF and Diary Card / Memory Aid terms

CRF term	Diary Card / Memory Aid term
Cough	Cough
Fever	Temperature measured as 100.4°F or higher
Anosmia	Loss of smell
Ageusia	Loss of taste
Chillblains	Pain, redness, sores in your fingers and toes exposed to cold
Difficulty breathing	Difficulty breathing
Shortness of breath	Feeling short winded
Pneumonia	Infection of the lungs
Stroke	Stroke
Myocarditis	Heart inflammation
Myocardial infarction	Heart attack
Thromboembolic event	Blood clots
Purpura fulminans	A type of purplish skin rash
Pharyngitis	Sore Throat
Chills	Chills
Myalgia	Muscle aches and pains
Headache	Headache
Rhinorrhea	Runny nose
Abdominal Pain	Belly pain
Nausea	Feeling queasy
Diarrhea	Loose stools
Vomiting	Throwing up

Virologically-confirmed COVID-19 illness

Virologically-confirmed COVID-19 illness is defined as a positive result for SARS-CoV-2 by Nucleic Acid Amplification Test (NAAT) on a respiratory sample in association with a COVID-19-like illness.

Serologically-confirmed SARS-CoV-2 infection

Serologically-confirmed SARS-CoV-2 infection is defined as a positive result in serum for presence of antibodies specific to non-Spike protein of SARS-CoV-2 detected by ELISA.

8.2.2.2 COVID-19-like Illness Surveillance

Passive Surveillance

Following randomization and vaccination all participants will be instructed to contact the site if they experience symptoms of a COVID-19-like illness at any time during the study.

Active Surveillance

Following randomization and vaccination, active surveillance will be used to identify potential COVID-19 clinical illness cases.

All participants will be contacted by study site or delegated call center D57 (2 weeks after D43 contact) after vaccination and continuing until D181 (Cohort 1) or D202 (Cohort 2). The frequency of contacts will be once every 2 weeks. Prior to these specified time-points, active surveillance will still occur during the established contacts (phone calls and visits) as described in the SoA. After active surveillance has ended at D181 (Cohort 1) or D202 (Cohort 2), passive surveillance will continue through the end of the study as previously stated above.

Collection of respiratory samples

For the duration of the study, the site will arrange for a respiratory sample to be taken if the participant experiences symptoms of COVID-19-like illness (see [Section 8.2.2.1](#)). The respiratory sample will be obtained as soon as possible from the onset of clinical manifestations of COVID-19-like illness.

Reporting of events temporally associated with a COVID-19-like illness

In addition to obtaining a respiratory sample, the site will collect detailed information about the symptoms, severity and duration of illness, as well as information on healthcare utilization events (hospitalizations, emergency room visits, and non-routine office visits [including urgent care visits]) and medication use (eg, antibiotics, antivirals).

In the event of hospitalization during the course of illness, detailed information on the course of the illness including duration of symptoms, oxygen requirements, laboratory tests, imaging investigations (including computerized tomography), use of mechanical ventilation and other respiratory support medications used, and outcome will be collected.

In the event that a respiratory sample swab cannot be collected, the research site will still obtain the above information. All participants reporting a COVID-19-like illness will have a 30-day follow-up telephone call.

8.2.2.3 SARS-CoV-2 Nucleoprotein Antibody Serum IgG ELISA

SARS-CoV-2 anti-nucleoprotein antibodies will be measured using an ELISA. Microtiter plates will be coated with SARS-CoV-2 nucleoprotein antigen diluted in coating buffer to the optimal concentration.

Plates may be blocked by the addition of a blocking buffer to all wells and incubation for a defined period. Following incubation, plates will be washed. All controls, reference, and samples will be pre-diluted with dilution buffer. The pre-diluted controls, reference and samples will then be further serially diluted in the wells of the coated test plate.

The plates will be incubated for a defined period. Following incubation, plates will be washed, an optimized dilution of goat anti-human IgG enzyme conjugate will be added to all wells, and plates will be further incubated. Following this incubation, the plates will be washed, and enzyme substrate solution will be added to all wells. Plates will be incubated for a defined period to allow the substrate to develop. Substrate development will be stopped by the addition of a stop solution to each well. An ELISA microtiter plate reader will be used to read the test plates using assay specific SoftMax Pro templates.

The average OD value for the plate blank will be subtracted from all the ODs within each plate. The sample titers will be derived using the measured values of the blanks, controls, and the reference standard curve, which will be included on each assay plate within the run.

8.2.2.4 Nucleic Acid Amplification Test (NAAT) for COVID-19 Case Detection

In the assay, respiratory samples will be collected, and the RNA is extracted. The purified template is then evaluated by an NAAT using SARS-CoV-2 specific primers to specifically amplify SARS-CoV-2 targets.

8.3 Safety Assessments

This section presents safety assessments other than AEs which are presented in [Section 8.4](#).

Planned time points for all safety assessments are provided in the SoA ([Section 1.3](#)).

8.3.1 Medical History

Prior to enrollment, participants will be assessed for pre-existing conditions and illnesses, both past and ongoing. Any such conditions will be documented in the source document. Significant (clinically relevant) medical history (reported as diagnosis) including conditions/illnesses for which the participant is or has been followed by a physician or conditions/illnesses that could resume during the course of the study or lead to an SAE or to a repetitive outpatient care will be collected in the CRF.

8.3.2 Physical Examinations

At designated visits, the Investigator or a delegate will perform a targeted physical examination based on the participant's medical history and the examiner's medical judgment. Information will be recorded in the source document.

8.3.3 Vital Signs

Oral pre-vaccination temperature and other vital signs will be systematically collected by the Investigator on the source document. Tympanic, skin, and temporal artery thermometers must not be used.

8.3.4 Clinical Safety Laboratory Assessments

Urine pregnancy testing will be performed in women of childbearing potential before each vaccination.

- See [Appendix 10.2](#) for the list of clinical laboratory tests to be performed and to the SoA for the timing and frequency.
- The Investigator must review the laboratory report, document this review, and record any clinically relevant changes occurring during the study in the AE section of the CRF. The laboratory reports must be filed with the source documents. Clinically significant abnormal laboratory findings are those which are not associated with the underlying disease, unless judged by the Investigator to be more severe than expected for the participant's condition.
- All laboratory tests with values considered clinically significantly abnormal during participation in the study or after the last injection of study intervention should be repeated until the values return to normal or baseline or are no longer considered clinically significant by the Investigator or medical monitor.
 - If such values do not return to normal/baseline within a period of time judged reasonable by the Investigator, the etiology should be identified and the Sponsor notified.
 - All protocol-required laboratory assessments, as defined in [Appendix 10.2](#), must be conducted in accordance with the laboratory manual/operating guidelines and the SoA.
 - If laboratory values from non-protocol specified laboratory assessments performed at the institution's local laboratory of choice require a change in participant management or are considered clinically significant by the Investigator (eg, SAE or AE), then the results must be recorded in the CRF.

8.4 Adverse Events and Serious Adverse Events

Safety will be described in all study participants.

The definitions of an AE, SAE, and the different categories of AEs can be found in [Appendix 10.3](#).

AEs will be reported by the participants to the investigator, then by the Investigator to the Sponsor.

The Investigator and any qualified designees are responsible for detecting, documenting, and recording events that meet the definition of an AE or SAE and remain responsible for following up AEs that are serious, considered related to the study intervention or study procedures, or that caused the participant to discontinue the study (see [Section 7](#)).

An ESDR will be performed for Sentinel Safety Cohort participants. The goal of ESDR is to allow the preliminary safety assessment for a cautious, step-wise approach to vaccine administration, starting with participants aged 18-49 years, as there is no previous human data for the CoV2 preS dTM candidate vaccine.

Sentinel Safety Cohort

The participants' enrollment will include the following sequential steps:

- Step 1:
 - Thirty participants aged 18-49 years from Cohort 1 will be enrolled in the Sentinel Safety Cohort, whereafter enrollment will be paused.
 - Six participants will be randomly assigned to each of the 5 dosing groups defined in Cohort 1: 5 µg and 15 µg AF03-adjuvanted groups, 5 µg and 15 µg AS03-adjuvanted groups, and placebo.
 - Early safety data collection is planned 8 days after the completion of the vaccination (D09, including safety laboratory data); and ESDR is to be planned as soon as possible. Limited members of the Sponsor Study Team (RMO, Biostatistician and Programmer, Pharmacovigilance Science Expert, and Global Safety Officer) will review unblinded safety data and will provide their recommendation to continue the recruitment.
- Step 2: If there is no safety signal after the ESDR after the completion of the vaccination in Sentinel Safety Cohort, recruitment will reopen to all dosing groups and both age strata.

ESDR

The safety data collected for ESDR for Sentinel Safety Cohort will be reviewed by the Investigator. The intensity of non-serious AEs/adverse reactions (ARs) will be assessed using the Sanofi Pasteur scale.

The following safety parameters will be assessed as part of the early safety data review for the Sentinel Safety Cohort participants after the first injection of CoV2 preS dTM candidate vaccine:

- Immediate reactions
- Solicited injection site and systemic reactions
- Laboratory abnormalities (including hematology, chemistry, coagulation time, and urinalysis)
- Unsolicited AEs reported as vaccine related by the Investigator
- SAEs and AESIs

If any of the below criteria are met, the data on the particular alert threshold event will be reviewed by the SMT and a decision will be made as to whether subsequent vaccinations in the study will be allowed to resume. Enrollment will be paused during the ESDR, and the following safety parameters will be examined:

- ≥ 2 participants per dosing group (n=6) experiencing Grade 3 systemic reaction (without concurrent infectious disease)
- ≥ 2 participants per dosing group (n=6) experiencing Grade 3 solicited injection site pain
- ≥ 2 participants per dosing group (n=6) experiencing Grade 3 unsolicited non serious reactions (reactions not explained by any other possible etiology)
- ≥ 2 participants with Grade 3 laboratory AE (Grade 3 abnormality if Grade 1 or 2 at baseline) of the same type (reactions not explained by any other possible etiology)

- ≥ 2 participants with Grade 2 laboratory AE (Grade 2 abnormality if normal at baseline) of the same type (reactions not explained by any other possible etiology) and judged by the Investigator to be clinically meaningful
- Any related SAEs

Following the ESDR and resumption of enrollment and dosing, occurrence of any one of these criteria will result in a pause in enrollment and vaccination pending Sponsor decision. The study status and final Sponsor decision will be submitted for notification to the IRB/IEC.

Halting Rules throughout the Study

Blinded safety data will be reviewed by limited members of the Sponsor Study Team (RMO, Biostatistician and Programmer, Pharmacovigilance Science Expert, and Global Safety Officer) at regular intervals to identify any new safety signals or safety concerns during the conduct of the study. A pause might be recommended in both recruitment and/or further vaccination while it investigates any potential signal or concern.

Enrollment will be paused during the review and the data will be examined if:

- Any of the following events, assessed as related to the vaccine by the Investigator and the Sponsor, are reported in the study:
 - SAE
 - New Onset of Potential immune-mediated diseases (pIMDs)
 - Ulceration, abscess or necrosis at the injection site
 - Four or more participants across treatment groups experience the same Grade 3 AE of the same type in the absence of any other etiology
 - Two or more participants across treatment groups experience the same Grade 3 laboratory abnormality assessed by the investigator as clinically significant
- Any of the following events, suggestive of vaccine associated enhanced disease, are detected in the study including:
 - Any death due to SARS-CoV-2 infection
 - $> 10\%$ of the study population is hospitalized due to SARS-CoV-2 infection
 - ≥ 4 ICU admissions among participants ≥ 50 years due to SARS-CoV-2 infection
 - ≥ 8 ICU admissions among participants 18-49 years due to SARS-CoV-2 infection

Case unblinding may be performed if necessary.

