The blind will be broken by the Sponsor at the time of the ESDR (with access to study intervention assignments [for the Sentinel Safety Cohort participants only] to a limited number of Sponsor Study Staff members comprising the Core Safety Management Team) and at the time of the first interim analysis after the first database lock. However, participant-level data will be maintained blinded on site until the end of the study/until the interim Clinical Study Report approval.

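### Read literally, the two laboratory pause criteria in Protocol 8.4 miss a shift from normal at baseline to Grade 3; the gap is only partly covered by the other safety rules

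*Protocol*

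**What the plan says.** Protocol Section 8.4 lists criteria that send a safety finding in the Sentinel Safety Cohort to the safety management team. Two concern laboratory results. Each needs at least two participants with no other explanation for the result, and neither is restricted to one dosing group:

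- a "Grade 3 laboratory AE (Grade 3 abnormality if Grade 1 or 2 at baseline) of the same type";
- a "Grade 2 laboratory AE (Grade 2 abnormality if normal at baseline) of the same type", which the Investigator must also judge clinically meaningful.

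The criteria stay in force after the ESDR: "occurrence of any one of these criteria will result in a pause in enrollment and vaccination pending Sponsor decision".

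A second set, the halting rules for the whole study, follows in the same section. Its automatic action is "Enrollment will be paused during the review and the data will be examined if" a listed event occurs. One listed event is "Two or more participants across treatment groups experience the same Grade 3 laboratory abnormality assessed by the investigator as clinically significant". It carries no baseline condition, but it sits under events that both Investigator and Sponsor assess as vaccine-related. For vaccination the same text is permissive: "A pause might be recommended in both recruitment and/or further vaccination while it investigates any potential signal or concern".

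**The concern.** Each laboratory criterion has a parenthesis that fixes the baseline state. Grade 3 is tied to a Grade 1 or 2 baseline and Grade 2 to a normal baseline, and neither says 'or higher'. A participant who goes from normal to Grade 3 therefore fits neither.

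The resulting order is perverse. On the Table 10.4 scale, two participants going from normal ALT to 3 times the upper limit of normal (Grade 2) can trip the rule if this is judged clinically meaningful. Two going from normal to 6 times the limit (Grade 3) cannot.

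The study enrolls healthy adults, so a normal baseline is probably the commonest starting point; this is an inference, as the documents give no rate. There is no independent data monitoring committee (Section 9.6), so the written triggers carry more weight than they otherwise would. At stake is whether second injections in Cohort 2 stop automatically or only on the sponsor's recommendation.

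**Working it through.** **1. Every upward shift against the two criteria.**

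| Baseline | Post-baseline | Grade 3 criterion | Grade 2 criterion |
|---|---|---|---|
| Normal | Grade 1 | no | no |
| Normal | Grade 2 | no | yes, if clinically meaningful |
| Normal | Grade 3 | **no** | **no** |
| Grade 1 | Grade 2 | no | no |
| Grade 1 | Grade 3 | yes | no |
| Grade 2 | Grade 3 | yes | no |

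Three of six shifts are counted. Of the three uncounted, two end at Grade 1 or 2 and need not trigger a pause. Normal to Grade 3 is the only uncounted shift that ends at Grade 3.

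**2. Intent.** Section 10.8 explains that the count in the Grade 3 criterion was lowered from 3 to 2 because 3 would have been less strict than the overall halting rules. The overall laboratory rule accepts any baseline, so for this one shift the criterion is still the less strict of the two. The clinical filters are similar: the criterion counts a laboratory AE, and Protocol 8.3.4 and 10.3.1 and SAP 4.4.1.3 tie AE status to clinical relevance or significance.

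**3. What else would act on two same-type normal-to-Grade-3 cases.**

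- *Overall halting rule:* pauses enrollment if the cases are clinically significant and related. First injections are given on the day of enrollment, so they stop too. Second injections do not stop automatically.
- *Grade 3 unsolicited-reaction criterion (Section 8.4):* a clinically significant laboratory abnormality is an unsolicited AE, so this could fire and, after the ESDR, would pause vaccination. It needs two cases in the same dosing group. Section 10.3.5.1.2 also grades such events on a general interference-with-activity scale, so a Grade 3 value on Table 10.4 without symptoms may not be a Grade 3 AE.
- *DCI04 (Section 7.1.2):* stops one participant's second injection after a related Grade 3 AE that the investigator judges to pose unreasonable or significant risk. It does not pause the study.

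**4. Who could be affected (Table 4.2).**

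- Cohort 1: 5 × 20 + 5 × 10 = 150; less 30 sentinels = 120 enrolled after the ESDR.
- Cohort 2: (20 + 60 + 20 + 60 + 20 + 20) + (10 + 30 + 10 + 30 + 10) = 200 + 90 = 290 second injections.
- Cohort 2 placebo: 20 + 10 = 30, leaving 290 − 30 = 260 second vaccine injections.
- Check: 150 + 290 = 440.

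Scheduled results that could meet a trigger while second injections remain come from the 120 Cohort 1 participants at D09 and the earlier Cohort 2 participants at D30. Second injections fall at D22, with a window of +7 days. Once the last participant is enrolled, an enrollment pause stops nothing, while second injections can stay due for 21 to 28 days.

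**5. Illustration only.** The documents give no rate of new Grade 3 values, so assume a rate r per laboratory parameter and a share s of these cases with a normal baseline. With n = 30 sentinels, P(at least 2) = 1 − (1 − p)^n − np(1 − p)^(n−1), where p = r(1 − s) as worded and p = r with normal included.

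| r | As worded, s = 70% | As worded, s = 90% | As worded, s = 100% | With normal included |
|---|---|---|---|---|
| 2% | 0.014 | 0.002 | 0 | 0.120 |
| 5% | 0.074 | 0.010 | 0 | 0.447 |
| 10% | 0.227 | 0.036 | 0 | 0.816 |

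This is the chance that the written criterion is met, not the chance that reviewers notice the cases.

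**The case against.** The strongest reply is that the criteria are alert thresholds: a participant who reaches Grade 3 from normal has passed Grade 2 on the way, and the Grade 3 parenthesis only sets a higher bar for an already abnormal baseline. That may be what was meant, but the text does not say it. The Grade 2 parenthesis plainly limits the baseline, and the Grade 3 one has the same form.

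The second reply is that the safeguards make the gap harmless. During the ESDR this largely stands. Enrollment is already paused after 30 sentinels, and the unblinded reviewers are "a limited number of Sponsor Study Staff members comprising the Core Safety Management Team", so a trigger would refer the finding to people already looking at all laboratory abnormalities. The next step is also conditional: "If there is no safety signal after the ESDR after the completion of the vaccination in Sentinel Safety Cohort, recruitment will reopen". After the ESDR it stands in part. The overall rule, the unsolicited-reaction criterion and DCI04 each catch some cases, and the sponsor may still recommend a vaccination pause. None guarantees one when the cases fall in different dosing groups.

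A reader might infer that two normal-to-Grade-3 cases would go unnoticed, or that 290 people were exposed to unchecked dosing. The documents support neither. The cases would be visible to the reviewers, a clinically significant and related pair would still pause enrollment, and 290 is every planned Cohort 2 second injection, not an expected number affected. Nor is there support for a deliberate omission; Section 10.8 points the other way.

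**Conclusion.** The point holds as a minor defect in a written safety rule, probably a drafting slip. The uncovered part is the automatic pause of vaccination after the ESDR when normal-to-Grade-3 cases are spread across dosing groups or are not rated Grade 3 on the general AE scale. It bears only on Cohort 2 second injections still outstanding, with an upper bound of 290 (260 vaccine, 30 placebo). The true number would be smaller, because some would already have been given when a trigger arose. No frequency can be attached, since the documents give no rate of Grade 3 laboratory shifts.

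This rests on the literal reading of both parentheses, and on the unsolicited-reaction criterion carrying over after the ESDR as a per-group count.

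**What to change.** Change the Grade 3 parenthesis to: *Grade 3 abnormality if normal, Grade 1 or Grade 2 at baseline*. The rule that applies after the ESDR refers back to the same criteria, so it is corrected at the same time.

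The cost is one added word and no new data. The downside is an occasional extra review. Glucose, for example, is collected nonfasting (Table 10.1) but graded on a fasting scale with Grade 3 above 125 mg/dL (Table 10.4), so a meal could move a participant from normal to Grade 3. The AE and other-etiology judgments already in the criterion would have to filter this.

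For this study the change probably comes too late. The first interim analysis used safety data to D43, a partial database lock had taken place by Amendment 1 (Protocol 9.5), and SAP 5.1.2.4 says the formulation is not being taken further. The wording should be corrected in any later protocol that reuses these rules. The toxicity-grade shift summary already planned in SAP 5.1.1.2 will show whether any such shifts occurred, so no extra analysis is needed.
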